### 7.4.3 Data entry and verification

In order to ensure the accuracy of the data, two data administrators check the data independently. For any questions in the case report form, the data administrators generate the question answer form (DRQ) and send it to the researcher through clinical research associate. The researchers recheck the data and reply in time, and the data administrators revise and input the data accordingly.

### 7.4.4 Data audit and database locking

After all questions of the data in the system are resolved, the principal investigator, statistician and data administrator first review the data and determine the association of adverse events and study, then determine the analyzed data set, last lock the audited data without any change. If there is any question after the database lock, it should be corrected in the statistical analysis process, and be recorded in detail.

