## 6. Safety evaluation

6.1 Adverse events: Any adverse medical events occurring during the study period are defined as adverse events, such as drug reactions, adverse reactions associated with ovarian stimulation, complications associated with pregnancy, and other discomfort complaints

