#### 6.2 Adverse events report:

Mild adverse events are recorded in the progress note.

Serious adverse events are submitted to Medicine Ethics Committee within 48 hours of occurrence.

6.3 Safety indexes are adverse events occurring in the treatment group and the control group, such as gastrointestinal reactions and allergies.

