9.3 Risk control measures

9.3.1 Subjects are fully informed and sign informed consent before participation.

9.3.2 If serious adverse events occur, stop the study immediately and report to the department and Medicine Ethics Committee in the first time, and control the impact of adverse events to a minimum.

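### The only relatedness judgement described for adverse events comes at the pre-lock data review, shared with non-clinical roles and with no masking stated

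*Combined protocol and SAP*

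**What the plan says.** Section 7.4.4 sets an order of steps before lock. It begins "After all questions of the data in the system are resolved". At that point "the principal investigator, statistician and data administrator first review the data and determine the association of adverse events and study", and the group goes on to "then determine the analyzed data set, last lock the audited data without any change".

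Section 6 covers adverse events as they arise. Section 6.1 is broad: "Any adverse medical events occurring during the study period are defined as adverse events". Its examples include drug reactions, reactions to ovarian stimulation and complications of pregnancy. Section 6.2 gives two routes: "Mild adverse events are recorded in the progress note", and "Serious adverse events are submitted to Medicine Ethics Committee within 48 hours of occurrence". Section 6.3 adds "Safety indexes are adverse events occurring in the treatment group and the control group", with gastrointestinal reactions and allergies as examples. Section 9.3.2 says "If serious adverse events occur, stop the study immediately and report to the department and Medicine Ethics Committee in the first time".

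On masking, section 4 describes the design as randomized and controlled and does not mention blinding. RECO-18 is four pills a day; the control is one tablet a day of a named brand, with no dummy. Under section 5.5 the investigator assigns women from the sealed envelope. Section 7.1 asks that major protocol violations be defined before database lock and unblinding, but no section says who is blinded or how.

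**The concern.** Relatedness is a clinical judgement. It depends on when the event began relative to product intake, stimulation and embryo transfer, on what else the woman was taking, and on whether the event resolved. The clinician who sees her knows these things best at the time. The plan describes the judgement only at the end, from cleaned data, by a group in which two of the three roles (statistician and data administrator) are not clinical by title. By then the pregnancy outcomes are in the database, and at least one member can be presumed to know the arm.

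At stake is the credibility of any statement about which events were caused by RECO-18. A label set late and with the arm known can move in either direction. The same conditions apply to the next step, the choice of analysis set, which also bears on efficacy.

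**Working it through.** There is no stated figure to reproduce and no arithmetic to run: the documents give no adverse-event rate, no causality scale and no safety power. The check is a comparison of sections.

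1. **Is there an earlier relatedness judgement?** Section 6.1 defines adverse events without reference to cause. Section 6.2 says where mild events are written and when serious events are sent to the Ethics Committee. Section 6.3 names the safety indexes. Section 7.3 describes summaries of laboratory results and vital signs. Sections 7.4.2 and 7.4.3 cover form completion and queries. Section 9.3.2 covers serious events. None names an assessor, a scale or a time for relatedness. Section 7.4.4 is the only step described.

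2. **Related to what?** Section 7.4.4 refers to association with the study. Section 6.1 mixes three sources (product, stimulation, pregnancy), and the plan does not say which of them the judgement should separate.

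3. **What information reaches the review?** Mild events go to the progress note. Section 7.4.1 builds the database on the case report form. Whether the timing details needed for a causality judgement get from one to the other is not stated. Events that are neither mild nor serious have no described route.

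4. **Who may know the arm?** Envelope assignment by the investigator (5.5), together with four pills against one branded tablet (section 4), makes it reasonable to presume that the principal investigator knows the arm. The status of the statistician and the data administrator is not stated. The unblinding mentioned in 7.1 implies that someone is masked until then. These passages do not fit together as written.

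5. **What depends on the label?** The 48-hour report in 6.2 and the action in 9.3.2 are triggered by occurrence, so neither waits for relatedness. The index in 6.3 is events occurring in each group, so it stays the same whatever the label. A related-event summary is not named; it could enter only under the other safety indicators that 7.3 leaves to be summarised as appropriate.

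6. **What else does the group decide?** It fixes the analysis set. The full analysis set in 7.1 follows mechanically from randomization and receipt of treatment. The per-protocol set depends on major violations that are not yet defined, so this is where knowledge of arm or outcome could matter.

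7. **Do the serious-event timelines agree?** Section 6.2 gives 48 hours from occurrence. Section 9.3.2 asks for immediate reporting. They differ and need to be reconciled.

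**The case against.** The strongest reply is that this is a gap in documentation and does not endanger patients. A reader might infer that causality is judged too late to protect the women in the trial. The documents do not support that: serious events are reported and acted on because they occur, and reporting before causality is judged is the more cautious order. Adverse events are also collected from V2 to V6, and 6.1 lists drug reactions as a type, so nothing prevents staff from recognising one when it happens. This part of the reply stands.

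A reader might also infer that the reviewers are known to be unmasked. That is a fair presumption for the principal investigator only; for the other two roles the plan is silent, and 7.1 points the other way. Nor can a minimum delay be derived by adding up the full visit schedule, because section 5.8.7 ends follow-up at day 14 after transfer when the pregnancy test is negative. A shift in the arm comparison cannot be sized either: the comparison that 6.3 names counts all events.

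The case report form is not among the documents and might carry a relatedness field, with 7.4.4 only a final check of what was recorded. That is possible, but the wording of 7.4.4 has the group determine the association, not confirm it. Progress notes and signed queries do preserve some detail, which softens the point without assigning the judgement to a clinician at the time of the event.

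**Conclusion.** The point holds in a limited form. The only relatedness judgement the plan describes is made at the pre-lock review, jointly by three roles of which two are non-clinical by title, and the same group then fixes the analysis set. No masking is described, and the reference to unblinding in 7.1 conflicts with the rest of the plan.

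The harm is confined to two things. Relatedness labels are set late, possibly with arm and outcome known; and a pattern of non-serious reactions has no described relatedness assessment as it emerges. Serious-event reporting and all-event counts by arm are unaffected. No numerical size can be given. The conclusion assumes that no document outside those supplied, such as the case report form, already requires a relatedness judgement when the event is reported, and that an investigator who opens the envelope knows the arm. It is an inexpensive improvement worth making and does not call the primary analysis into question.

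**What to change.** - **Section 6:** have a physician investigator record relatedness on the case report form when the event is reported, separately for study product, ovarian stimulation and pregnancy, on a scale fixed in advance.
- **Section 7.4.4:** remove the causality decision from the group. Limit the pre-lock review to completeness and coding, and make it and the analysis-set decision from listings that do not show the arm. Allow a change of causality only by the physician, through a signed query.
- **Safety summary:** keep all-causality counts by arm as the main summary, with related events secondary.
- **Masking:** state who is masked and until when, and reconcile this with the unblinding mentioned in 7.1.
- **Serious events:** reconcile the reporting timelines in 6.2 and 9.3.2.

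The cost is a few extra form fields and changes of wording. No visits are added and treatment does not change.

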## 8. Quality Management

8.1 The research team has rich clinical experience and has received GCP training in order to conform to the protocol and ethical requirements

8.2 Animal experiments have shown that RECO18 significantly improved the fertility of mice, which sets the foundation for clinical research.

8.3 Reco-18 is a food for special dietary use based upon "National Food Safety Standard and Nutritional Supplementary Food for Pregnant and Lactating Women" (GB31601-2015). It contains multiple micronutrients (vitamins and minerals) and active constituent of Reco-18, and has passed through food inspection by a third party. Production license number is SC11337082906741.

## 9. Pre-assessment of risks and benefits and risk control preplan

### 9.1 Potential benefits

9.1.1 Subjects may get more opportunities for pregnancy with the participation in the study. Meanwhile the study may provide indirect benefit for other patients and generate social benefits

9.1.2 Researchers may develop an adjuvant therapy to improve the fertility of infertility patients, so as to benefit the majority of patients.

9.1.3 Medical institution may provide efficient service for patients, and raise the visibility.

9.2 Potential risks

9.2.1 For researchers and medical institution, the study may not meet the expectation and achieve the research purpose, resulting in the waste of medical resources.

9.2.2 For the patients, the fertility of the subjects may not be ultimately improved.

9.3 Risk control measures

9.3.1 Subjects are fully informed and sign informed consent before participation.

9.3.2 If serious adverse events occur, stop the study immediately and report to the department and Medicine Ethics Committee in the first time, and control the impact of adverse events to a minimum.

